6.2.1 Rationale for Patient Population

The patient population taking part in the study will comprise patients aged ≥ 18 years in first treatment for advanced FL, in which Obinutuzumab are administered in combination with chemotherapy during the induction phase, followed by Obinutuzumab maintenance therapy. This indication and treatment scheme is that approved by the EMA as per EU countries agency and AIFA as per Italian local agency.

6.2.2 Recruitment Procedure

No specific procedures for recruitment (e.g. advertisements, published information or other) were used for the study.

The Principal Investigator or a co-investigator in each investigational site will verify the eligibility of each patient for the participation in the study based on adherence to inclusion/exclusion criteria. Eligible patients who signed the ICF were then included in the study.

6.2.3 Dosage, Administration, and Compliance

Dosing and treatment duration of any studied medicinal products collected as parts of this non-interventional study are at the discretion of the physician in accordance with local clinical practice and local labelling.

6.2.4 Concomitant Medication and Treatment

Concomitant medication prescribed for concomitant diseases and treatment for untreated advanced FL at the beginning of the observation period or introduced during the observation period will be documented in the eCRF from start of therapy with Obinutuzumab until discontinuation of the treatment, if applicable.

6.3 VARIABLES

Only variables, obtained according to routine clinical practice (with exception of quality of life questionnaires) and collected according to the study objectives can and should be documented in this study.

6.3.1 Primary Effectiveness Variable

Progression of disease at 2 years (POD24), defined as the time from the date of treatment initiation with Obinutuzumab until the first documented progression of disease or death due to disease progression, whichever occurs first, within 24 months from the start of treatment with Obinutuzumab. Patients who have no disease progression and have not died due to disease progression or who are lost to follow-up at the time of analysis will be censored at the date of last tumor assessment where no progression was documented or the last date of follow-up for disease, whichever is last. Patients without post-baseline tumor assessments will be censored at the time of their baseline visit unless death due to disease progression occurs prior to their first scheduled tumor assessment. Patients who die for reasons not related to the disease progression within 24 months from the treatment start with Obinutuzumab will be excluded from the statistical analysis of the endpoint.

Moreover, the POD24 will be also analyzed as binary variables. Number and percentage of patients with its 95% confidence interval for POD24 will be calculated.

6.3.2 Secondary Effectiveness Variable

- Progression free survival (PFS) at 2 and 3 years, defined as the time from the date of treatment initiation until the first documented progression of disease measured by routine clinical care or death from any cause, whichever occurs first. Patients who have no disease progression and have not died or who are lost to follow-up at the time of analysis will be censored at the date of last tumor assessment where no progression was documented or the last date of follow-up for disease, whichever is last. Patients without post-baseline tumor assessments will be censored at the time of their baseline visit unless death occurs prior to their first scheduled tumor assessment;
- Time to next treatment (TTNT), defined as the Time to initiation of subsequent systemic anti-cancer therapy following initiation of Obinutuzumab containing therapy. Patients not starting a subsequent systemic anti-cancer therapy will be censored at the date of the last study visit;
- Overall survival (OS), defined as the time from initiation of study treatment to death from any cause. Patients who still alive at the time of analysis and patients who are lost to follow-up will be censored at their last time known to be alive;
- Correlation between POD24 and OS;
- TTLCB, defined as the time from first dose to loss of clinical benefit as assessed by the treating physician (single or multiple reasons possible: e.g. disease progression, deterioration in ECOG PS, death, other). Patients who do not loss clinical benefit will be censored at the date of the last study visit. Patients without post-baseline tumor assessments will be censored at the time of their baseline visit unless death occurs prior to their first scheduled tumor assessment;
- Overall response rate (ORR);
- Complete response (CR);
- Complete response at 30 months (CR30);
- Duration of response (DoR) measured per clinical practice, defined as the time from first documentation of CR or partial response (PR) (whichever occurs first) until disease progression, as evaluated by the physician according to routine clinical practice or death. Patients who have no disease progression and have not died or who are lost to follow-up at the time of analysis will be censored at the date of last tumor assessment where no progression was documented or the last date of follow-up for disease, whichever is last;
- Time to response, defined as the time from first dose of Obinutuzumab to first documented response as assessed in clinical routine. Patients without response at the time of analysis and patients who are lost to follow-up will be censored at the date of their last tumour assessment. Patients without post-baseline tumor assessments will be censored at the time of their baseline visit unless death occurs prior to their first scheduled tumor assessment;

- Rate of patients with stable disease (SD);
- Effectiveness of Obinutuzumab in different patient subgroups, stratified by FLIPI (intermediate/high), ECOG-PS, age at study entry, hepatitis infection (history of past/resolved infection or latent HBV after prophylaxis as per standard treatment guidelines), chemotherapy backbone choice, presence of autoimmune disease, history of renal failure and liver failure;
- FDG-PET response at end of induction and end of maintenance, as per clinical practice. When PET is not performed, the alternative routine tumor assessment method will be collected.

6.3.3 Safety Variables

- Incidence, nature, seriousness, severity and relatedness of all adverse events (AEs) and serious adverse events (SAEs);
- Infusion related reactions (IRRs) management at each center as per clinical practice;
- Clinical laboratory abnormalities;
- Adverse events of special interest (AESI);
- Vital signs.

6.3.4 Other Variables of Interest

- Patient/disease characteristics: age, sex, ECOG PS, Ann Arbor staging, FLIPI (intermediate/high), medical history and history of FL, comorbidities, physical examination and vital signs;
- Treatment pattern:
 - Time from diagnosis to start of treatment with Obinutuzumab;
 - Duration of treatment with Obinutuzumab;
 - Dose modifications;
 - Treatment discontinuation;
 - Prophylaxis medications;
 - Type of chemotherapy chosen in association with Obinutuzumab;
 - Second line regimens prescribed for patients who progressed within two years after starting first line therapy;
 - Time to initiation of subsequent systemic anti-lymphoma therapy following initiation of Obinutuzumab containing therapy;
 - Adherence to treatments
- Quality of life: EuroQol 5-Dimension Questionnaire, 5-level version (EQ-5D-5L); Functional Assessment of Chronic illness Therapy-Lymphoma (FACT-Lym);

- Presence of B symptoms;
- Concomitant medication prescribed or in current use from the start of therapy with Obinutuzumab until discontinuation of the treatment.
- *effectiveness of Obinutuzumab in real word setting;*
- *prescription profile*
- *COVID-19 impact on therapy adherence*

6.4 DATA SOURCES

6.4.1 Collection of Data on the CRF

Patients' data will be recorded on eCRFs. The degree of detail and completeness of data collected is dependent on local clinical practice. Data from patient notes should be entered on the CRF as soon as they become available. Data entered in the eCRF will not act as source documents.

6.4.2 Data Collected during the Observation Period

During therapy with Obinutuzumab, laboratory assessments are routinely performed in accordance with current guidelines and local standard of care. When performed during the observational period, available results that represent an adverse event in accordance to CTCAE vs. 5, relevant symptom/signal of an event or abnormal laboratory finding that results in a change of the treatment in study will be documented in the eCRF. Most data will be documented during the treatment period when the respective assessments are usually performed according to standard of care. The proposed assessments and suggested timings for assessments in the protocol/observational plan are not mandatory. It is up to the treating physician to perform and document the assessments as performed in the real clinical setting.

In the routine care setting, patients are seen regularly by their treating physicians either for treatment or for regular assessment after treatment. Thus, no study-specific visits or evaluations are required by this protocol.

Tumor assessments collected in eCRF will comprise the following periods as available:

- Baseline tumor assessment
- During induction:
 - Mid induction: tumor assessment performed between cycle 2 and cycle 4 after the start of treatments
 - End induction: tumor assessment performed at the day of cycle 6 /8 (or when induction is early discontinued) until 2 month later
- After induction treatment:
 - 1 year after the start of treatment (from 10 to 14 months after the start of treatment)

- 2 years after the start of treatment (from 22 to 26 months after the start of treatment)
- 3 years after the start of treatment (from 34 to 40 months after the start of treatment)
- 1 year after end of maintenance as applicable
- Any tumor assessment, and the method used that shows disease progression, CR or CRu during induction or maintenance.

The lack of tumor assessments in those periods are not a protocol deviation as clinical practice should be followed.

Since the enrolment of patients into the study will occur after the treatment has already started (Patients included should have performed at least 2 cycles of induction treatment with Obinutuzumab but no later than the completion of 1 year of the treatment with Obinutuzumab), a retrospective data collection is expected.

Retrospective data applicable to the study includes but not limits to the following information available before ICF signature (enrolment):

- Information regarding previous cycles performed with Obinutuzumab and chemotherapy (at least 2 cycles and no longer than 1 year of treatment)
- Safety data
- Baseline condition (before start of the treatment)
- Medical history
- Relevant laboratory exams
- Concomitant medication and procedures
- Diagnostic information
- Tumor assessments and cancer history
- Imaging exams
- Demographic Data
- Physical exams, performance status and FLIPI classification

Data will be collected as availability in source document.

Safety data will be provided as aggregate data for retrospective visits. Minimal information such as the event term, seriousness classification and reason, relationship and duration of the event will be collected as available. For prospective data collection of safety, additional variables will be collected as available, such as grade, outcome, concomitant treatment, background causality, onset and end date.

Quality of life will be evaluated by means of the EuroQol 5-Dimension Questionnaire, 5-level version (EQ-5D-5L), and of the Functional Assessment of Chronic illness Therapy-Lymphoma (FACT-Lym).

The EuroQol 5-Dimension Questionnaire, 5-level version (EQ-5D-5L) (Appendix 4), is a validated self-report health status questionnaire that is used to calculate a health status utility score for use in health economic analyses (*EuroQol Group 1990; Brooks 1996; Herdman et al. 2011*).

The Functional Assessment of Chronic illness Therapy-Lymphoma (FACT-Lym) (*Webster et al, 2005*) (Appendix 5) is used to assess quality of life in patients with various forms of lymphoma. It contains 42 items (questions) covering quality of life, common lymphoma symptoms and treatment side-effects. The questionnaire begins with the Functional Assessment of Cancer Therapy - General (FACT-G), which contains 27 items covering four core quality of life subscales: Physical Wellbeing (7 items), Social/Family Wellbeing (7), Emotional Wellbeing (6), and Functional Wellbeing (7). The FACT-Lym also includes an Additional Concerns subscale (15 items), addressing issues typically experienced by lymphoma patients. Some of the issues covered include pain, itching, night sweats, trouble sleeping, fatigue and trouble concentrating. The FACT-Lym also asks patients about their concerns about lumps and swelling, fevers, infections, weight, appetite, emotional stability and treatment.

To ensure instrument validity and that data standards meet health authority requirements, questionnaires scheduled for administration during a clinic visit will be completed in their entirety by the patient prior to the performance of non-PRO assessments and the *treatment administration of study treatment* (where applicable).

Patients will use an electronic PRO (ePRO) device to capture PRO data on the same day of clinic visits. The ePRO device and/or instructions for completing the PRO questionnaires electronically will be provided by the investigator staff. The data will be transmitted via a pre-specified transmission method (e.g., web or wireless) automatically after entry to a centralized database at the ePRO vendor. The data can be accessed by the appropriate sponsor study personnel securely via the Internet.

In case patient is not able to complete the electronic questionnaires, e.g. due to technical issues, the PRO data will be completed by patient in paper records and later transferred into the electronic system by site staff. In case any survival follow-up contact is conducted by phone or in case of patient's compromised reading ability (e.g illiterate patients/ vision issues, etc) the PRO data for that visit will be collected in an interview performed by a trained site staff (via telephone or face-to-face, depending on how visit occurs), recorded in paper records (source document) and then transferred in electronic system.

PRO questionnaires (FACT-Lym, EQ-5D) should be administered *on Day 1 of alternate cycles during induction treatment period and at each cycle during maintenance treatment period. PRO Questionnaires should be administered on Day 1 of the cycle prior to any treatment and assessments, i.e. PRO questionnaires should be collected only when*

corresponding to a treatment cycle. PRO questionnaires should also be administered at first visit after reporting disease progression.

Please see Appendix 2 for the data collection overview (as per standard of care).

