Data Collection (available data will be collected; no additional diagnostic or monitoring procedures will be applied to patients outside of routine clinical practice)	Enrolment visit ^a	Retrospective Data collection	Prospective Data Collected during Treatment Period (Induction and maintenance period)	Follow-up period ^b
Informed consent ^c	x			
Diagnosis confirmation (clinical stage, histology)		x		
Target Population	x	x		
Medical history and demographic data		x		
Concomitant treatments/medications ^d	x	x	x	
Treatment with Obinutuzumab	(x) ^e	(x) ^c	x	
Prophylaxis medication	x	x	x	
Laboratory assessments ^e	x	x	x	
Pregnancy test	x ^f	x ^f	x ^f	
Physical examination and Vital signs	x	x	x	
ECOG	x	x	x	x
B symptoms	x	x	x	x
QoL (Quality of life: EuroQol 5-Dimension Questionnaire, 5-level version (EQ-5D-5L); Functional Assessment of Chronic illness Therapy-Lymphoma (FACT-Lym) ^g	x		x	*
Chemotherapy regimen	x	x	x	
AEs/SAEs/AESI/SSIRR/ADR	x		x	x ^k
Retrospective Safety data collection		x ^h		
Tumor assessments	x	x	x	x
Ann Arbor	x	x		
FLIPI score assessment ⁱ	x	x		
BM evaluation	x	x	x	x
Response rate ^j	x	x	x	x
New anti-cancer therapy and survival status after end of treatment				x

^a Items Concomitant treatments/medications, Treatment with obinutuzumab, Pregnancy test. Physical examination and Vital signs, Prophylaxis medication and Chemotherapy regimen apply only for patients still on treatment at the time of enrollment as part of their standard procedures for treatment. In case of patients

enrolled after treatment completion, these data will be collected as indicated in the Retrospective column and the prospective information will be collected as described in the Follow-up period.

^b Approximately one-year follow-up after last dose of Obinutuzumab administration, as per clinical practice, or for patients that early discontinue the treatment up to 3.5 years after first treatment administration or until withdrawal of consent, study termination by the Sponsor, or death, whichever occurs first, regardless of whether patients start a new anti-cancer therapy. For patients that discontinue treatment before completing induction or maintenance, the follow up parameters can be collected in accordance with current patient's schedule visit and not every 2 months. Follow-up data will include at least tumor assessments, *new anti-lymphoma therapy informations*, and safety data.

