^c Patients included should have performed at least 2 cycles of induction treatment with Obinutuzumab and chemotherapy, within 1 year from beginning of treatment

^d Including any medication used by the patient from 7 days prior to starting treatment with obinutuzumab.

^e Laboratory tests will include: haematology (WBCs and differential count [at least neutrophils and monocyte %], RBCs, haemoglobin, haematocrit, platelet count) and blood chemistry (creatinine, beta-2 microglobulin, LDH, AST, ALT).

^f Data collected if performed per clinical practice as clinically indicated.

^g QoL will be completed prospectively period, every 2 cycles in induction treatment phase and every 2 months during maintenance treatment phase. For further instructions over QoL completion please refer to section 6.6.1. PRO questionnaires (FACT-Lym, EQ-5D) should be administered *on Day 1 of alternate cycles during induction treatment period and at each cycle during maintenance treatment period. PRO Questionnaires should be administered on Day 1 of the cycle* prior to any treatment and assessments, i.e. *PRO questionnaires should be collected only when corresponding to a treatment cycle.* PRO questionnaires should also be administered at first assessment after report of disease progression.

^h AEs/SAEs/AESI/SSIRR/ADR that occur prior ICF signature should be reported in eCRF as available; however only the event preferred term as per CTCAE vs 5.0 is required as Individual Case Safety Report are not applicable. Prospective safety that must be fully assessed and reported by study physician including assessment of seriousness (see Section 8.1.1.2), severity (see Appendix 3), and causality (see Appendix 3).

ⁱ FLIPI score (age, number of nodal sites, LDH level, haemoglobin, stage) or FLIPI2 (age, beta-2 microglobulin, bone marrow involvement, longest diameter of largest involved node, haemoglobin) collected at diagnosis.

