3.3.2 Laboratory and vital signs

Relevant laboratory and vital signs (*Systolic and diastolic blood pressure, Heart rate, Body temperature*) data will be displayed by time.

Additionally, all laboratory data will be summarized by grade with use of NCI CTCAE v5.0.

For each parameter the change from baseline to each post-baseline visit will be calculated.

All medications reported will be coded using the WHO-DRL Dictionary version 2018 or higher and classified according to 3rd level ATC level subgroup and Preferred Term.

The following vital signs, when performed as per clinical practice, will be captured in the eCRF:

- Systolic and diastolic blood pressure (mmHg)

- Heart rate (bpm)
- Body temperature (°C)

For each variable the change from baseline to each post-baseline visit will be calculated.

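### Protocol 6.4.2 and Appendix 2 give different rules for which laboratory results are entered; if 6.4.2 is followed, the planned change-from-baseline and grade summaries lean to the adverse side

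*Protocol*

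**What the plan says.** **Which results are entered.** Protocol 6.4.2 describes laboratory tests done as routine care during the observational period. It lists "available results that represent an adverse event in accordance to CTCAE vs. 5, relevant symptom/signal of an event or abnormal laboratory finding" and continues "that results in a change of the treatment in study will be documented in the eCRF". That gives three triggers, each depending on the result. The same section leaves the rest to the site: "It is up to the treating physician to perform and document the assessments as performed in the real clinical setting".

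Protocol Appendix 2 sets no such condition. Its table header reads "available data will be collected; no additional diagnostic or monitoring procedures will be applied to patients outside of routine clinical practice". The laboratory row is ticked for enrolment, the retrospective period and the prospective treatment period. Footnote e begins "Laboratory tests will include: haematology (WBCs and differential count [at least neutrophils and monocyte %], RBCs, haemoglobin, haematocrit, platelet count" and goes on to blood chemistry. SAP Appendix 1 repeats the table header, the row and the footnote.

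Data from before enrolment fall under a third description in 6.4.2, "Relevant laboratory exams", subject to what the source documents hold. What counts as relevant is not defined.

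**What is analysed.** SAP 3.3.2 states: "For each parameter the change from baseline to each post-baseline visit will be calculated", and also that "all laboratory data will be summarized by grade with use of NCI CTCAE v5.0". Protocol 6.7.2 plans the same two summaries. SAP section 3 summarises continuous data by mean, SD, median, interquartile range and range. SAP 3.6 has no method for missing data, and SAP 3.4 plans no sensitivity analysis.

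**The concern.** A change-from-baseline table describes the patients seen at a visit only if the decision to record a value does not depend on that value. Under the 6.4.2 triggers it does: a result that is an adverse event, signals one, or changes treatment is entered, and an unremarkable result need not be. The recorded post-baseline values then over-represent the abnormal tail. Mean change moves in the adverse direction, and the proportion in the higher grades rises if the denominator is recorded results.

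The study runs at about 50 sites with two written rules. Some sites may enter whole panels and others abnormal results alone, and the pooled tables would not show which. Baseline adds to this. Patients enrol after at least two cycles and up to one year into treatment, so baseline and early on-treatment values come under the separate retrospective wording. A change score may subtract values recorded under different rules.

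At stake is the reading of the laboratory safety tables, in a study where safety is a stated objective.

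**Working it through.** **The plan's own figures.** The documents give no figure on laboratory recording or on the size of any laboratory change. The design figure reproduces (39/300 gives an exact 95% interval of 9.41 to 17.34, width 7.93; stated 9.4 to 17.3, width 7.9), but it concerns POD24 and does not bear on this point.

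**Assumed inputs (none is in the documents).**
- True mean change is 0, with normal distributions and equal SD at baseline and post-baseline.
- Every patient has a recorded baseline, and the trigger lies on one side of the distribution, taken here as low values.
- q = share of post-baseline results meeting a 6.4.2 trigger, 5% to 30%.
- r = share of the other results that are entered anyway: 0 is a strict reading of 6.4.2, 1 is the Appendix 2 reading.
- ρ = correlation of baseline with post-baseline value, 0.3 to 0.7.

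**Formulas, in units of the SD of change.** Let c be the normal quantile of q and φ(c) the normal density there.
1. Selection on the change itself, r = 0: shift = −φ(c)/q.
2. Selection on the post-baseline value, r = 0: E[Y − X | Y < c] = −(1 − ρ)φ(c)/q. Dividing by the SD of change, √(2(1 − ρ)), gives −√((1 − ρ)/2) × φ(c)/q. The factor √((1 − ρ)/2) is 0.59 at ρ = 0.3 and 0.39 at ρ = 0.7.
3. Selection on the change with share r of the others entered: shift = −φ(c)(1 − r)/[q + (1 − q)r]. This is 0 when r = 1.

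| q | φ(c) | On change, r = 0 | On value, ρ = 0.3 | On value, ρ = 0.7 | On change, r = 0.5 |
|---|---|---|---|---|---|
| 5% | 0.1031 | −2.06 | −1.22 | −0.80 | −0.10 |
| 10% | 0.1755 | −1.75 | −1.04 | −0.68 | −0.16 |
| 20% | 0.2800 | −1.40 | −0.83 | −0.54 | −0.23 |
| 30% | 0.3477 | −1.16 | −0.69 | −0.45 | −0.27 |

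Example: q = 30%, r = 0.5 gives −0.3477 × 0.5/(0.30 + 0.35) = −0.27.

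**Grade summary.** If the denominator is recorded results, trigger results make up q/[q + (1 − q)r] of them. With q = 10%:
- r = 0.5: 0.10/0.55 = 18%
- r = 0.25: 0.10/0.325 = 31%
- r = 0.1: 0.10/0.19 = 53%

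The true share is 10% throughout. The SAP does not state the denominator.

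**The case against.** A reader might infer that 6.4.2 restricts entry to abnormal results and that the laboratory tables are therefore biased by a large amount. The documents do not establish that. The word only does not appear in 6.4.2. Appendix 2 of the Protocol and Appendix 1 of the SAP point to full panels. Other text fits full entry as well: Protocol 6.8.5 puts local laboratory ranges in the eCRF, and Protocol 6.7.2 converts values to SI units and identifies Grade 3 and 4 values within the displayed data. If sites enter everything available, there is no selection.

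A reader might also infer that mildly abnormal results go unrecorded. That goes too far. The trigger is an adverse event under CTCAE v5, and the scale in Protocol Appendix 3.1 starts at Grade 1, mild or asymptomatic. Protocol Appendix 3.3.5 says that not every abnormality is an adverse event, so some mild results may be left out, but 6.4.2 sets no severity threshold.

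The planned reporting is also close to what is needed. SAP 2.4.2 defines the laboratory variable as abnormalities. The output list in SAP Appendix 2 has a summary of laboratory abnormalities and names no laboratory change table. The mean enters only through the general rule in SAP section 3. The study is descriptive with no hypothesis tests, and adverse events are summarised separately.

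All of this stands and makes the point conditional and limited. It does not remove it. Naming which available results are documented serves little purpose unless others may be left out. The change and grade summaries are written into both documents, and SAP 3.7 does not list result-dependent recording among the limitations.

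**Conclusion.** The documents contradict each other on which laboratory values reach the eCRF, and the planned summaries are sound under one rule only. The bias is conditional:
- **6.4.2 followed strictly:** an adverse shift of about 0.45 to 2.1 SD of change with no true change, for 5% to 30% of results meeting the trigger.
- **Half of the other results also entered:** about 0.1 to 0.3 SD when selection is on the change, and smaller when it is on the value.
- **All available results entered:** zero.
- **Sites differ:** a mixture that the tables cannot separate.

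The direction follows from the wording of 6.4.2. The sizes rest entirely on the assumed shares, correlation, normality and one-sided trigger, and should not be read as a forecast. The POD24 estimate and the sample size are unaffected. The correction should be made before the laboratory tables are interpreted.

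**What to change.** Reconcile Protocol 6.4.2 with Protocol Appendix 2 and SAP Appendix 1, by one of two routes.

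**(a) Record everything available.** Amend 6.4.2 so that every available result of the Appendix 2 panel is entered whatever its value. Keep the change-from-baseline tables and show the number of patients with a value at each visit. Cost: a protocol amendment and more data entry at the sites, including back-entry for patients already enrolled when the rule changes.

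**(b) Keep the 6.4.2 rule.** State it in the appendix footnotes, and delete the laboratory change-from-baseline summary from both Protocol 6.7.2 and SAP 3.3.2; changing the SAP alone would leave it at odds with the Protocol. Replace the grade summary by the number and percentage of safety-population patients with at least one recorded abnormality, by worst CTCAE grade. This matches the laboratory abnormality output already listed in SAP Appendix 2. Cost: wording changes in both documents and no laboratory change tables. Patients with no laboratory entry would count as having no recorded abnormality, which a footnote should say.
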